5.2.5 Timing of Dose Administration

Trial MK-3475 treatment (100 or 200 mg fixed dose) should be administered on Day 1 of each cycle after all procedures/assessments have been completed as detailed on the Trial Flow Chart (Section 7.0). MK-3475 treatment may be administered up to 3 days before or after the scheduled Day 1 of each cycle due to administrative reasons. Subjects may be dosed no less than 18 days from the previous dose. If treatment is held for greater than 3 cycles (or 63 days) subject will be withdrawn from investigational product treatment permanently.

All trial treatments will be administered on an outpatient basis unless the patient is currently admitted to the hospital for another purpose which does not exclude treatment with BCG or MK-3475 or enrollment into the study.

MK-3475 will be administered as a 30 minute IV infusion (treatment cycle intervals may be increased due to toxicity as described in Section 5.2.3.3). Sites should make every effort to target infusion timing to be as close to 30 minutes as possible. However, given the variability of infusion pumps from site to site, a window of -5 minutes and +10 minutes is permitted (i.e., infusion time is 30 minutes: -5 min/+10 min).

The Procedure Manual contains specific instructions for MK-3475 dose calculation, reconstitution, preparation of the infusion fluid, and administration.

5.2.6 Trial Blinding/Masking

This is an open-label trial; therefore, the Sponsor, Investigator and subject will know the treatment administered.

5.3 Concomitant Medications/Vaccinations (allowed & prohibited)

Medications or vaccinations specifically prohibited in the exclusion criteria are not allowed during the ongoing trial. If there is a clinical indication for one of these or other medications or vaccinations specifically prohibited during the trial, discontinuation from trial therapy or vaccination may be required. The Investigator should discuss any questions regarding this

with the Sponsor. The final decision on any supportive therapy or vaccination rests with the Investigator and/or the subject's primary physician. However, the decision to continue the subject on trial therapy or vaccination schedule requires the mutual agreement of the Investigator, the Sponsor, and the subject.

5.3.1 Acceptable Concomitant Medications

All treatments that the Investigator considers necessary for a subject's welfare may be administered at the discretion of the Investigator in keeping with the community standards of medical care. All concomitant medication will be recorded on the case report form (CRF), including all prescription, over-the-counter (OTC), herbal supplements, and IV medications and fluids. If changes occur during the trial period, documentation of drug, dosage, frequency, route, and date should also be included on the CRF.

All concomitant medications received within 28 days before the first dose of trial treatment and 30 days after the last dose of trial treatment should be recorded. Concomitant medications administered after 30 days after the last dose of trial treatment should be recorded for SAEs and ECIs as defined in Section 9.0.

5.3.2 Prohibited Concomitant Medications

Subjects are prohibited from receiving the following therapies during the Screening and Treatment Phase (including retreatment for post-complete response relapse) of this trial:

- Anti-cancer systemic chemotherapy or biological therapy
- Immunotherapy not specified in this protocol
- Chemotherapy not specified in this protocol
- Investigational agents other than MK-3475
- Radiation therapy
- Live vaccines within 30 days prior to the first dose of trial treatment and while participating in the trial. Examples of live vaccines include, but are not limited to, the following: measles, mumps, rubella, chicken pox, yellow fever, rabies, BCG (with the exclusion of BCG for treatment), and typhoid (oral) vaccine. Seasonal influenza vaccines for injection are generally killed virus vaccines and are allowed; however, intranasal influenza vaccines (e.g. Flu-Mist[®]) are live attenuated vaccines and are not allowed.
- Glucocorticoids for any purpose other than to modulate symptoms from an event of clinical interest of suspected immunologic etiology. The use of steroids for treatment of a grade 1 or 2 immune mediated adverse event may delay BCG treatment for up to 2 weeks with the expectation that steroid treatment will be discontinued prior to the next BCG treatment cycle. A delay of longer than 2 weeks will permanently discontinue the

patient from BCG treatment within the study or permanent withdrawal of the patient from the study. The choice will be at the discretion of the treating Investigator. Steroid treatment for grade 3 or higher immune mediated events will require discontinuation of BCG treatment and/or withdrawal from the study.

- The use of physiologic doses of corticosteroids may be approved after consultation with the Sponsor.
- Drug combinations containing immunosuppressants and/or bone marrow depressants and/or radiation. The above mentioned therapies interfere with the development of the immune response and should not be used in combination with BCG.
- Antimicrobial therapy may interfere with the effectiveness of BCG treatment. If antimicrobial therapy is required, BCG treatment should be delayed as appropriate.

Subjects who, in the assessment by the Investigator, require the use of any of the aforementioned treatments for clinical management should be removed from the trial treatment or delayed in the case of antimicrobial treatment. Subjects may receive other medications that the Investigator deems to be medically necessary.

The Exclusion Criteria describes other medications which are prohibited in this trial.

There are no prohibited therapies during the Post-Treatment Follow-up Phase.

5.4 Rescue Medications & Supportive Care

5.4.1 Supportive Care Guidelines

Subjects should receive appropriate supportive care measures as deemed necessary by the treating investigator. Suggested supportive care measures for the management of adverse events with potential immunologic etiology are outlined below. Where appropriate, these guidelines include the use of oral or intravenous treatment with corticosteroids as well as additional anti-inflammatory agents if symptoms do not improve with administration of corticosteroids. Note that several courses of steroid tapering may be necessary as symptoms may worsen when the steroid dose is decreased. For each disorder, attempts should be made to rule out other causes such as metastatic disease or bacterial or viral infection, which might require additional supportive care. The treatment guidelines are intended to be applied when the Investigator determines the events to be related to pembrolizumab.

Note: If after the evaluation the event is determined not to be related, the Investigator does not need to follow the treatment guidance (as outlined below). Refer to Section 5.2.1 for dose modification.

It may be necessary to perform conditional procedures such as bronchoscopy, endoscopy, or skin photography as part of evaluation of the event.

- **Pneumonitis:**

- For **Grade 2 events**, treat with systemic corticosteroids. When symptoms improve to Grade 1 or less, steroid taper should be started and continued over no less than 4 weeks.
- For **Grade 3-4 events**, immediately treat with intravenous steroids. Administer additional anti-inflammatory measures, as needed.
- Add prophylactic antibiotics for opportunistic infections in the case of prolonged steroid administration.

- **Diarrhea/Colitis:**

Subjects should be carefully monitored for signs and symptoms of enterocolitis (such as diarrhea, abdominal pain, blood or mucus in stool, with or without fever) and of bowel perforation (such as peritoneal signs and ileus).

- All subjects who experience diarrhea/colitis should be advised to drink liberal quantities of clear fluids. If sufficient oral fluid intake is not feasible, fluid and electrolytes should be substituted via IV infusion. For Grade 2 or higher diarrhea, consider GI consultation and endoscopy to confirm or rule out colitis.
- For **Grade 2 diarrhea/colitis**, administer oral corticosteroids.
- For **Grade 3 or 4 diarrhea/colitis**, treat with intravenous steroids followed by high dose oral steroids.
- When symptoms improve to Grade 1 or less, steroid taper should be started and continued over no less than 4 weeks.

- **Type 1 diabetes mellitus (if new onset, including diabetic ketoacidosis [DKA]) or \geq Grade 3 Hyperglycemia, if associated with ketosis (ketonuria) or metabolic acidosis (DKA)**

- For **T1DM** or **Grade 3-4 Hyperglycemia**
 - Insulin replacement therapy is recommended for Type I diabetes mellitus and for Grade 3-4 hyperglycemia associated with metabolic acidosis or ketonuria.
 - Evaluate patients with serum glucose and a metabolic panel, urine ketones, glycosylated hemoglobin, and C-peptide.

- **Hypophysitis:**

- For **Grade 2 events**, treat with corticosteroids. When symptoms improve to Grade 1 or less, steroid taper should be started and continued over no less than 4 weeks. Replacement of appropriate hormones may be required as the steroid dose is tapered.

- For **Grade 3-4** events, treat with an initial dose of IV corticosteroids followed by oral corticosteroids. When symptoms improve to Grade 1 or less, steroid taper should be started and continued over no less than 4 weeks. Replacement of appropriate hormones may be required as the steroid dose is tapered.

- **Hyperthyroidism or Hypothyroidism:**

Thyroid disorders can occur at any time during treatment. Monitor patients for changes in thyroid function (at the start of treatment, periodically during treatment, and as indicated based on clinical evaluation) and for clinical signs and symptoms of thyroid disorders.

- **Grade 2** hyperthyroidism events (and **Grade 2-4** hypothyroidism):
 - In hyperthyroidism, non-selective beta-blockers (e.g. propranolol) are suggested as initial therapy.
 - In hypothyroidism, thyroid hormone replacement therapy, with levothyroxine or liothyronine, is indicated per standard of care.
- **Grade 3-4** hyperthyroidism
 - Treat with an initial dose of IV corticosteroid followed by oral corticosteroids. When symptoms improve to Grade 1 or less, steroid taper should be started and continued over no less than 4 weeks. Replacement of appropriate hormones may be required as the steroid dose is tapered.

- **Hepatic:**

- For **Grade 2** events, monitor liver function tests more frequently until returned to baseline values (consider weekly).
 - Treat with IV or oral corticosteroids
- For **Grade 3-4** events, treat with intravenous corticosteroids for 24 to 48 hours.
- When symptoms improve to Grade 1 or less, a steroid taper should be started and continued over no less than 4 weeks.

- **Renal Failure or Nephritis:**

- For **Grade 2** events, treat with corticosteroids.
- For **Grade 3-4** events, treat with systemic corticosteroids.
- When symptoms improve to Grade 1 or less, steroid taper should be started and continued over no less than 4 weeks.

- **Management of Infusion Reactions:**

Signs and symptoms usually develop during or shortly after drug infusion and generally resolve completely within 24 hours of completion of infusion.

Table 4 below shows treatment guidelines for subjects who experience an infusion reaction associated with administration of pembrolizumab (MK-3475).

- **Supportive Care for Suspected Primary Adrenal Insufficiency**

If symptoms are suggestive of an endocrinopathy and the patient is not in adrenal crisis, endocrine laboratory results should be evaluated before corticosteroid therapy is initiated. Endocrine work-up will include TSH and free T4 levels to determine if thyroid abnormalities are present. TSH, prolactin, ACTH, and a morning cortisol level will help to differentiate primary adrenal insufficiency from primary pituitary insufficiency. Grade 1 or 2 endocrine toxicity without adrenal crisis may resolve spontaneously if a patient has no or minimal symptoms, but patients will be monitored closely, with guidance from an endocrinologist; otherwise, short-term, high-dose corticosteroids (e.g., dexamethasone 4 mg every six hours or equivalent) with relevant hormone replacement (e.g., levothyroxine, hydrocortisone, sex hormones) will be administered. Patients in adrenal crisis (characterized by a constellation of symptoms suggestive of severe dehydration, hypotension, or shock) will be treated as a medical emergency and given intravenous injections of glucocorticoids and large volumes of intravenous saline solution with dextrose.

Remainder of Page Intentionally Left Blank

Table 4: Infusion Reaction Treatment Guidelines

NCI CTCAE Grade	Treatment	Premedication at subsequent dosing
Grade 1 Mild reaction; infusion interruption not indicated; intervention not indicated	Increase monitoring of vital signs as medically indicated until the subject is deemed medically stable in the opinion of the Investigator.	None
Grade 2 Requires infusion interruption, but responds promptly to symptomatic treatment (e.g., antihistamines, NSAIDs, narcotics, IV fluids); prophylactic medications indicated for ≤ 24 hours	Stop infusion and monitor symptoms. Additional appropriate medical therapy may include, but is not limited to,: IV fluids Antihistamines NSAIDs Acetaminophen Narcotics Increase monitoring of vital signs as medically indicated until the subject is deemed medically stable in the opinion of the Investigator. If symptoms resolve within one hour of stopping drug infusion, the infusion may be restarted at 50% of the original infusion rate (e.g. from 100 mL/hr to 50 mL/hr). Otherwise, dosing will be held until symptoms resolve. The subject should be premedicated for the next scheduled dose. Subjects who develop Grade 2 toxicity despite adequate premedication should be permanently discontinued from further trial treatment administration.	Subject may be premedicated 1.5h (± 30 minutes) prior to infusion of MK-3475 with: Diphenhydramine 50 mg po (or equivalent dose of antihistamine). Acetaminophen 500-1000 mg po (or equivalent dose of antipyretic).
Grades 3 or 4 Grade 3: Prolonged (i.e., not rapidly responsive to symptomatic medication and/or brief interruption of infusion); recurrence of symptoms following initial improvement; hospitalization indicated for other clinical sequelae (e.g., renal impairment, pulmonary infiltrates) Grade 4: Life-threatening; pressor or ventilatory support indicated	Stop Infusion. Additional appropriate medical therapy may include, but is not limited to,: IV fluids Antihistamines NSAIDs Acetaminophen Narcotics Oxygen Pressors Corticosteroids Epinephrine Increase monitoring of vital signs as medically indicated until the subject is deemed medically stable in the opinion of the Investigator. Hospitalization may be indicated. Subject is permanently discontinued from further trial treatment administration.	No subsequent dosing
Appropriate resuscitation equipment should be available in the room and a physician readily available during the period of drug administration. For further information, please refer to the Common Terminology Criteria for Adverse Events v4.0 (CTCAE) at http://ctep.cancer.gov		

5.5 Diet/Activity/Other Considerations

5.5.1 Diet

Subjects should maintain a normal diet unless modifications are required to manage an AE such as diarrhea, nausea or vomiting.

5.5.2 Contraception

MK-3475 may have adverse effects on a fetus in utero. Furthermore, it is not known if MK-3475 has transient adverse effects on the composition of sperm.

For this trial, male subjects will be considered to be of non-reproductive potential if they have azoospermia (whether due to having had a vasectomy or due to an underlying medical condition).

Female subjects will be considered of non-reproductive potential if they are either:

(1) postmenopausal (defined as at least 12 months with no menses without an alternative medical cause; in women < 45 years of age a high follicle stimulating hormone (FSH) level in the postmenopausal range may be used to confirm a post-menopausal state in women not using hormonal contraception or hormonal replacement therapy. In the absence of 12 months of amenorrhea, a single FSH measurement is insufficient.);

OR

(2) have had a hysterectomy and/or bilateral oophorectomy, bilateral salpingectomy or bilateral tubal ligation/occlusion, at least 6 weeks prior to screening;

OR

(3) has a congenital or acquired condition that prevents childbearing.

Female and male subjects of reproductive potential must agree to avoid becoming pregnant or impregnating a partner, respectively, while receiving study drug and for 120 days after the last dose of study drug by complying with one of the following:

(1) practice abstinence[†] from heterosexual activity;

OR

(2) use (or have their partner use) acceptable contraception during heterosexual activity.

Acceptable methods of contraception are[‡]:

Single method (one of the following is acceptable):

- intrauterine device (IUD)

Product: MK-3475

Protocol/Amendment No.: Amendment 5, 21 October 2019

- vasectomy of a female subject's male partner
- contraceptive rod implanted into the skin

Combination method (requires use of two of the following):

- diaphragm with spermicide (cannot be used in conjunction with cervical cap/spermicide)
- cervical cap with spermicide (nulliparous women only)
- contraceptive sponge (nulliparous women only)
- male condom or female condom (cannot be used together)
- hormonal contraceptive: oral contraceptive pill (estrogen/progestin pill or progestin-only pill), contraceptive skin patch, vaginal contraceptive ring, or subcutaneous contraceptive injection

†Abstinence (relative to heterosexual activity) can be used as the sole method of contraception if it is consistently employed as the subject's preferred and usual lifestyle and if considered acceptable by local regulatory agencies and ERCs/IRBs. Periodic abstinence (e.g., calendar, ovulation, sympto-thermal, post-ovulation methods, etc.) and withdrawal are not acceptable methods of contraception.

‡If a contraceptive method listed above is restricted by local regulations/guidelines, then it does not qualify as an acceptable method of contraception for subjects participating at sites in this country/region.

Subjects should be informed that taking the study medication may involve unknown risks to the fetus (unborn baby) if pregnancy were to occur during the study. In order to participate in the study, subjects of childbearing potential must adhere to the contraception requirement (described above) from the day of study medication initiation (or 14 days prior to the initiation of study medication for oral contraception) throughout the study period up to 120 days after the last dose of trial therapy. If there is any question that a subject of childbearing potential will not reliably comply with the requirements for contraception, that subject should not be entered into the study.

5.5.3 Use in Pregnancy

If a subject inadvertently becomes pregnant while on treatment with MK-3475, the subject will immediately be removed from the study. The site will contact the subject at least monthly and document the subject's status until the pregnancy has been completed or terminated. The outcome of the pregnancy will be reported to the Sponsor and to manufacturer's safety division without delay and within 24 hours if the outcome is a serious adverse experience (e.g., death, abortion, congenital anomaly, or other disabling or life-threatening complication to the mother or newborn). The study Investigator will make every

effort to obtain permission to follow the outcome of the pregnancy and report the condition of the fetus or newborn to the Sponsor. If a male subject impregnates his female partner, the study personnel at the site must be informed immediately and the pregnancy reported to the Sponsor and to manufacturer's safety division and followed as described above and in Section 9.1.2.

5.5.4 Use in Nursing Women

It is unknown whether MK-3475 is excreted in human milk. Since many drugs are excreted in human milk, and because of the potential for serious adverse reactions in the nursing infant, subjects who are breast-feeding are not eligible for enrollment.

5.6 Subject Withdrawal/Discontinuation Criteria

Subjects may withdraw consent at any time for any reason or be dropped from the trial at the discretion of the Investigator should any untoward effect occur. In addition, a subject may be withdrawn by the Investigator or the Sponsor if enrollment into the trial is inappropriate, the trial plan is violated, or for administrative and/or other safety reasons. Specific details regarding discontinuation or withdrawal are provided in Section 8.1.5.1.

5.7 Subject Replacement Strategy

Subjects who have been screened and enrolled will be included in an intent-to-treat population. However, if a subject has been enrolled and subsequently treated or attempted treatment (IV insertion with MK-3475 preparation) with at least 1 cycle of MK-3475, the patient will not be replaced. If a screened subject withdraws prior to first treatment cycle, that subject may be replaced.

5.8 Clinical Criteria for Early Trial Termination

Early trial termination will be the result of the criteria specified below:

1. Quality or quantity of data recording is inaccurate or incomplete
2. Poor adherence to protocol and regulatory requirements
3. Incidence or severity of adverse drug reaction in this or other studies indicates a potential health hazard to subjects

Stopping Rules:

The number of patients (15) planned for this study is not sufficient to represent the population as a whole nor is it sufficient to complete a powerful statistical analysis.

The first 3 subjects will be treated at 100 mg every 3 weeks for 6 cycles. If one subject of the three subjects requires the dose of MK-3475 be withheld or discontinued, the 100 mg cohort will be expanded to 6 subjects. If two out of three or two out of six subjects

develop toxicity that requires the dose to be withheld or discontinued, the dose will be not be escalated to 200 mg MK-3475 every 3 weeks. All remaining subjects will be treated at 100 mg MK-3475 every 3 weeks for 6 cycles.

For study subject safety, if there is any fatal toxicity or morbidity event related to the study treatment or procedures, or if one or more of the 15 subjects treated experience a grade 4 toxicity, then subject accrual will be suspended and all data pertaining to the events will be reviewed by the Study Investigators and Data Safety Review Team to determine if there is the need for any corrective actions.

Once that review is completed and any appropriate action is taken, subject accrual will begin again, if the Data Safety Review Team members have approved continuation of the study. If there is a second fatal treatment/morbidity event related to the study treatment or procedures, the study will be terminated. If 4 of 15 subjects experience grade 4 toxicities, the accrual will be suspended and reviewed for added appropriate measures. If 5 subjects experience grade 4 toxicity, the study will be terminated.

Non-local safety reports will be evaluated as they are received. Tabulations of the reports will be provided to the Data Safety Review Team with access to the full reports for completeness of review.

4. Plans to modify or discontinue the development of the study drug

In the event the investigational product is no longer available, ample notification will be provided so appropriate adjustments to subject treatment can be made.

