5.2.1.4 Risks/Adverse Effects of BCG Treatment

For specific information, please see package insert in Appendix C.

Common Side Effects ($\geq 20\%$)

- Dysuria (painful urination)
- Urinary frequency
- Flu-like symptoms
- Hematuria (blood in urine)
- Fever

Less Common Side Effects (4-20%)

- Malaise/ fatigue
- Cystitis (inflammation of the bladder)
- Urgency
- Nocturia
- Cramping or pain in bladder
- Chills
- Nausea
- Incontinence

Rare Side Effects (<4%)

- Anemia

BCG sepsis
BCG infection in other organs
Coagulopathy
Contracted Bladder
Epididymitis/prostatitis
Hepatic Granuloma
Hepatitis
Leukopenia
Orchitis
Pneumonitis
Urinary obstruction

Subjects may develop symptoms of bladder irritability related to the inflammatory response induced by BCG, as well as hematuria following BCG intravesicular treatment. The symptoms typically begin 4-6 hours after instillation and last 24-72 hours. The irritative side effects are usually seen following the third instillation, and tend to increase in severity after each administration. The irritative bladder adverse effects can usually be managed symptomatically with products such as pyridium, propantheline bromide, oxybutynin chloride and acetaminophen. Symptom management will be at the discretion of the treating Investigator. If the patient develops hematuria, then treatment must be postponed until urine is clear again. See dose modification/delay (section 5.2.1.5) for further instruction. No dose reduction or antibiotic treatment has been proven to prevent or decrease bladder irritation related to BCG.

Subjects may develop “Flu-like” symptoms (malaise, fever, and chills) which often reflect hypersensitivity reactions, and can be treated symptomatically with antihistamines (Prophylactic treatment with antihistamine before subsequent BCG courses is left to the discretion of the provider.).

The most serious complication of BCG is disseminated BCG sepsis with associated mortality. In addition, infections have been reported in lung, liver, bone, bone marrow, kidney, regional lymph nodes, and prostate in patients who have received intravesical BCG. Some male genitourinary tract infections (orchitis/epididymitis) have been resistant to multiple drug anti-tuberculous therapy and required orchiectomy. These complications were reported in less than 1% of patients.

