9.1.4 Evaluating Adverse Events

An Investigator who is a qualified physician will evaluate all adverse events according to the NCI Common Terminology for Adverse Events (CTCAE), version 4.0. Any adverse event which changes CTCAE grade over the course of a given episode will have each change of grade recorded on the adverse event case report forms/worksheets.

All adverse events regardless of CTCAE grade must also be evaluated for seriousness.

Remainder of Page Intentionally Left Blank

Table 8: Evaluating Adverse Events

An Investigator who is a qualified physician will evaluate all adverse events as to:

V4.0 CTCAE Grading	Grade 1	Mild; asymptomatic or mild symptoms; clinical or diagnostic observations only; intervention not indicated.
	Grade 2	Moderate; minimal, local or noninvasive intervention indicated; limiting age-appropriate instrumental ADL.
	Grade 3	Severe or medically significant but not immediately life-threatening; hospitalization or prolongation or hospitalization indicated; disabling; limiting self-care ADL.
	Grade 4	Life threatening consequences; urgent intervention indicated.
	Grade 5	Death related to AE
Seriousness	A serious adverse event is any adverse event occurring while the subject is enrolled into the study:	
	† Results in death ; or	
	† Is life threatening ; or places the subject, in the view of the investigator, at immediate risk of death from the event as it occurred (Note: This does not include an adverse event that, had it occurred in a more severe form, might have caused death.); or	
	† Results in a persistent or significant disability/incapacity (substantial disruption of one’s ability to conduct normal life functions); or	
	† Results in or prolongs an existing inpatient hospitalization (hospitalization is defined as an inpatient admission, regardless of length of stay, even if the hospitalization is a precautionary measure for continued observation. (Note: Hospitalization for an elective procedure to treat a pre-existing condition that has not worsened is not a serious adverse event. A pre-existing condition is a clinical condition that is diagnosed prior to the use of a Merck product and is documented in the patient’s medical history.); or	
	† Is a congenital anomaly/birth defect (in offspring of subject taking the product regardless of time to diagnosis); or	

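### Section 5.8 counts related deaths and Grade 4 subjects separately, so one related death plus four other Grade 4 subjects reaches no mandatory stop, while five Grade 4 subjects with no death do (minor)

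*Combined protocol and SAP*

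**What the plan says.** All the counts are in the Stopping Rules of section 5.8 and refer to the 15 planned subjects.

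- **Suspension.** Accrual is suspended for review "if there is any fatal toxicity or morbidity event related to the study treatment or procedures", or once any treated subject has a Grade 4 toxicity. It restarts only if the Data Safety Review Team has approved continuation.
- **Termination on deaths.** "If there is a second fatal treatment/morbidity event related to the study treatment or procedures, the study will be terminated".
- **Second review on Grade 4.** "If 4 of 15 subjects experience grade 4 toxicities, the accrual will be suspended and reviewed for added appropriate measures".
- **Termination on Grade 4.** "If 5 subjects experience grade 4 toxicity, the study will be terminated".
- **General criterion.** Criterion 3 in the same section lists this ground for early termination, with no count attached: "Incidence or severity of adverse drug reaction in this or other studies indicates a potential health hazard to subjects".

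Table 8 in section 9.1.4 defines Grade 5, separately from Grade 4, as "Death related to AE". Section 9.1.4 also states: "Any adverse event which changes CTCAE grade over the course of a given episode will have each change of grade recorded". Section 6.1 gives the Data Safety Review Team the task of enforcing the stopping rules and adds no combined count.

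**The concern.** The 4- and 5-subject sentences name Grade 4 only. Neither says Grade 4 or worse, and neither brings in a death. Replacing one of five Grade 4 subjects with a related death makes the outcome worse, yet it removes the automatic stop. The sponsor chose to take discretion away at five Grade 4 subjects. As written, the rule gives discretion back in a worse case with the same number of subjects affected, and the documents offer no reason for that ordering.

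Safety of the combination is the primary objective (section 3.1), and the Team has to apply these counts as written. A mandatory rule should not become more lenient as harm increases.

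**Working it through.** The plan states no error rate, target toxicity rate or operating characteristic for these counts, so there is no figure of its own to reproduce. The check has two parts.

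**1. Which outcomes are affected**

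Let d be the number of subjects with a related death and no recorded Grade 4 stage. Let g be the number of other subjects with Grade 4 toxicity, with d + g ≤ 15.

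- Rule as written: terminate if d ≥ 2 or g ≥ 5.
- Pooled rule: terminate if d ≥ 2 or d + g ≥ 5.

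| d | g | As written | Pooled |
|---|---|---|---|
| 0 | 4 | suspend, review | suspend, review |
| 0 | 5 | terminate | terminate |
| 1 | 3 | suspend, review | suspend, review |
| 1 | 4 | suspend, review | **terminate** |
| 1 | 5 | terminate | terminate |
| 2 | 0 | terminate | terminate |

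For the two rules to differ, d + g ≥ 5 must hold with d ≤ 1 and g ≤ 4. That leaves only d = 1, g = 4, and enumerating every pair confirms it. For the review at 4 subjects, the only state newly reached is d = 1, g = 3.

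**2. How likely that state is**

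The rates are assumptions: a related-death rate p_d of 0.5% or 1%, and a Grade 4 rate p_g of 10%, 20% or 30%. All 15 subjects are taken as treated and independent.

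P(1,4) = [15!/(1! 4! 10!)] × p_d × p_g⁴ × (1 − p_d − p_g)¹⁰, where the coefficient is 15 × 1001 = 15015.

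For p_d = 1% and p_g = 20%: 15015 × 0.01 × 0.0016 × 0.79¹⁰ = 0.24024 × 0.0947 = 0.0227.

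| Assumed p_d | p_g = 10% | p_g = 20% | p_g = 30% |
|---|---|---|---|
| 0.5% | 0.0025 | 0.0121 | 0.0160 |
| 1% | 0.0047 | 0.0227 | 0.0298 |

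The result depends strongly on the assumed death rate. At 2% the same cells are 0.0084, 0.0401 and 0.0514.

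**Effect of pooling at p_d = 1%.** The termination probability rises by exactly P(1,4), apart from rounding. The extra chance of reaching the review at 4 is P(1,3) = 5460 × p_d × p_g³ × (1 − p_d − p_g)¹¹, where 5460 = 15 × 364.

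| p_g | Terminate, as written | Terminate, pooled | P(1,3) |
|---|---|---|---|
| 10% | 0.0223 | 0.0270 | 0.0152 |
| 20% | 0.1729 | 0.1956 | 0.0327 |
| 30% | 0.4908 | 0.5205 | 0.0249 |

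**The case against.** **Separate thresholds are a legitimate design, and the state is already handled.** Two deaths against five Grade 4 subjects is a stricter rule for deaths. A related death suspends accrual, and so does the fourth Grade 4 subject. Team approval is a condition for restarting, and criterion 3 allows termination on judgement. A reader might infer that the trial would run on unchecked after a death and four Grade 4 subjects. The documents do not support that. What remains is the reversed ordering of the mandatory counts.

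**The fatal case may already count as Grade 4.** Each change of grade is recorded, so a death that passed through Grade 4, as a fatal sepsis plausibly would, could be the fifth Grade 4 subject. This narrows the gap to deaths with no recorded Grade 4 stage. However, 5.8 does not say whether a subject who dies is also counted at Grade 4, so the stop could depend on whether an intermediate grade was noted.

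**The fatal-event wording is loose.** If a non-fatal related morbidity event could be the second event, a death followed by a related Grade 4 event might already terminate the study. The fatal-only reading is the natural one, because the 4- and 5-subject counts would otherwise do little. It is still an assumption.

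**The rates have no anchor.** A reader might take the remark in section 5.2.1.4, "These complications were reported in less than 1% of patients", as support for a 1% death rate. It concerns complications of BCG alone, and which ones it covers is unclear. It is not a death rate, still less a rate of deaths that bypass Grade 4. This objection stands in full.

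**The stop would often come late.** If five affected subjects fall at random enrolment positions and events follow enrolment order, the fifth is on average at position 5 × 16/6 = 13.3. In 1001/3003, one third of cases, it is the last subject. This limits the benefit for accrual, though subjects still on treatment could gain.

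**Conclusion.** The point holds in a narrow form. The mandatory counts place one related death plus four Grade 4 subjects below five Grade 4 subjects with no death. That is a wrong ordering in the rule rather than a missing detail.

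It affects one outcome only. It rests on the fatal-only reading of the second-event sentence and on a death with no recorded Grade 4 stage. Under the assumed rates the state has probability of about 0.2% to 3.0%. Those values should not be read as chances of a trial continuing unchecked, because suspensions and Team decisions would intervene. The severity is minor.

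**What to change.** Reword the 4-subject and 5-subject sentences of 5.8 to count *subjects with Grade 4 toxicity, or with a fatal (Grade 5) event related to study treatment or procedures, each subject counted once*. Relatedness for deaths needs to be in the text itself, since Grade 4 or worse alone would also bring in unrelated deaths. Counting each subject once settles how to treat a fatal case that passed through Grade 4.

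Leave the second-fatal-event sentence and the suspension sentence as they are. The Grade 4 part of the count would still carry no relatedness condition, as now.

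The cost is two reworded sentences, with no new data, visits or subjects. Mandatory termination and the review at 4 would each come slightly earlier in a trial that already has a related death. At an assumed 1% death rate, termination probability rises by about 0.5, 2.3 and 3.0 percentage points for Grade 4 rates of 10%, 20% and 30%. The one added review state has probability 1.5%, 3.3% and 2.5% at the same rates.
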